4.4 End of Study Definition

The end of the study is defined as the date of last contact (related to this study) with the last participant who participates in this study (last participant's Safety Follow Up assessment shown in Section 1.3).

A participant has completed the study if he/she has completed all study parts, including Safety Follow Up assessments on Day 20 (Section 1.3).

Study Termination Criteria

The study will be discontinued or terminated if:

- Unacceptable risk, any relevant toxicity, or a negative change in the risk/benefit assessment is identified. This might include the occurrence of AEs whose character, severity or frequency is new in comparison to the existing risk profile.
- Any data derived from other clinical studies or toxicological studies become available which negatively influence the risk/benefit assessment.

General information on study termination is specified in [Appendix 2](#).

5 Study Population

The criteria in Sections 5.1 and 5.2 are designed to enroll only participants, who are appropriate for the study; thereby, ensuring the study fulfills its objectives. All relevant medical and nonmedical conditions are considered when deciding whether a participant is suitable for this study.

Prospective approval of protocol deviations to inclusion and exclusion criteria, also known as protocol waivers or exemptions, is not permitted.

Before performing any study assessments that are not part of the participant's routine medical care, the Investigator will confirm that the participant has provided written informed consent, as indicated in [Appendix 2](#).

5.1 Inclusion Criteria

Participants are eligible to be included in the study only if all the following criteria apply:

Category	Criterion
Age	1. Are between 18 and 55 (inclusive) years of age at the time of signing the informed consent.
Type of Participant and Disease Characteristics	2. Are overtly healthy as determined by medical evaluation, including no clinically significant abnormality identified by medical history, cardiac monitoring, physical examination or laboratory evaluation and no active clinically significant disorder, condition, infection or disease that would pose a risk to participant safety or interfere with the study evaluation, procedures, or completion at Screening and Day -1.
Weight	3. Have a body weight within 50 and 100 kg inclusive and BMI within the range ≥ 18.5 and ≤ 29.9 kg/m^2 (inclusive) at Screening.

Category	Criterion
Sex and Contraception/Barrier Requirements	
4. Are male or female (not a WOCBP)
 
The Investigator confirms that each participant agrees to use appropriate contraception and barriers, if applicable. The contraception, barrier, and pregnancy testing requirements are below.
 
Contraceptive use will be consistent with local regulations on contraception methods for those participating in clinical studies.
 
a. Male Participants:
 
Agree to the following during the study intervention period and for at least 1 week after the last dose of study intervention:
 
 • Refrain from donating fresh and unwashed sperm 
PLUS, either:
 
 • Abstain from intercourse with a WOCBP. 
OR
 
 • Use a male condom: 
 • When having sexual intercourse with a WOCBP, who is not currently pregnant, and instruct her to use a highly effective contraceptive method with a failure rate of < 1% per year, as described in Appendix 3, since a condom may break or leak. 
b. Not a WOCBP, confirmed at Screening, by fulfilling at least 1 of the following criteria:
 
 • Females who are postmenopausal (age-related amenorrhea \geq 12 consecutive months and increased FSH $>$ 40 mIU/mL). • Documentation of irreversible surgical sterilization by hysterectomy, or bilateral oophorectomy, or bilateral salpingectomy.
Informed Consent	
5. Capable of giving signed informed consent, as indicated in Appendix 2, which includes compliance with the requirements and restrictions listed in the ICF and this protocol.

Laboratory Parameters	
6. All values for hematology, coagulation, and biochemistry tests of blood and urinalysis within the normal range (at Screening and Day -1). Minor (solitary) nonclinically relevant excursion(s) are allowed as judged by the Investigator, however amylase and lipase should not exceed the ULN; ALT, AST and total bilirubin should not exceed the ULN \times 1.1.

ALT=alanine aminotransferase, AST=aspartate aminotransferase, BMI=body mass index, FSH=follicle stimulating hormone, ICF=informed consent form, ULN=upper limit of normal, WOCBP=woman of child-bearing potential.

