2.3.1 Risk Assessment

Based on the currently available nonclinical as well as clinical safety data for tepotinib, and the lack of genotoxicity in nonclinical studies, there is no objection against administration of single doses or short-term multiple administrations to healthy participants. The participants will be under close monitoring for e.g., potential AEs, safety laboratory parameters, ECG, and vital signs in the clinical research unit to reduce the risk for any untoward effects of tepotinib.

Exposure to tepotinib at different dose levels including 500 mg tepotinib HCl hydrate were well tolerated by healthy participants (refer to current tepotinib IB). Cumulatively, 702 patients and 225 healthy participants and participants with hepatic impairment were exposed to tepotinib (500 mg in the majority of studies in healthy participants and 30 mg and 100 mg each in 1 study) in interventional clinical studies sponsored by Merck or any affiliate (DSUR No. 9, reporting period 25 September 2020 to 24 March 2021, data lock point 24 March 2021).

No maximum tolerated dose could be defined in the first-in-man study EMR200095_001, using up to 1,400 mg once daily administered in 21-day cycles (refer to current tepotinib IB).

No single identified metabolic pathway comprises more than 25% of the administered dose (refer to current tepotinib IB). Therefore, the DDI potential with tepotinib as victim to inhibitors of coadministered CYP3A4 inhibitors is considered low.

Tepotinib is substrate to P-gp dependent transport. Assuming a worst case in which P-gp mediated biliary secretion accounts for 30% of the total clearance of tepotinib, the maximum AUC increase through complete inhibition of P-gp is 43% (refer to current tepotinib IB). The effect of combined inhibition of CYP3A4 and P-gp is unknown.

Identified and Potential Risks of Clinical Significance	Summary of Data/Rationale for Risk	Mitigation Strategy
Study Intervention(s) – Tepotinib		
Nonclinical Risks: Teratogenicity	CCI [REDACTED] [REDACTED] [REDACTED] [REDACTED] [REDACTED] [REDACTED] [REDACTED] [REDACTED] [REDACTED] [REDACTED] [REDACTED] [REDACTED]	CCI [REDACTED] [REDACTED] [REDACTED] [REDACTED] [REDACTED] [REDACTED] [REDACTED] [REDACTED] [REDACTED] [REDACTED] [REDACTED] [REDACTED]

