8.3.4 Pregnancy

- Details of all pregnancies in female partners of male participants will be collected after the start of study intervention and until at least 3 months after the last dose of study intervention.
- If a pregnancy is reported, the Investigator will record the pregnancy information on the appropriate form and submit it to the Sponsor within 24 hours of female partner of male participant (after obtaining the necessary signed informed consent from the female partner) pregnancy.
- While pregnancy itself is not considered to be an AE or SAE, any pregnancy complication or elective termination of a pregnancy will be reported as an AE or SAE. Adverse pregnancy outcomes (e.g., spontaneous abortion, fetal death, stillbirth, congenital anomalies, ectopic pregnancy) are considered and reported as SAEs. A spontaneous abortion (occurring at < 22 weeks gestational age) or stillbirth (occurring at > 22 weeks gestational age) is always considered to be an SAE and will be reported as such.
- The participant /pregnant female partner will be followed to determine the outcome of the pregnancy. The Investigator will collect follow-up information on the participant /pregnant female partner and the neonate, and the information will be forwarded to the Sponsor. Generally, follow-up will not be required for longer than 6 to 8 weeks beyond the estimated delivery date for a healthy newborn. In case of a congenital anomaly or other illness of the newborn, follow-up will continue until the illness has resolved or there is a definite outcome of the event.
- Any poststudy pregnancy related SAE considered reasonably related to the study intervention by the Investigator will be reported to the Sponsor as specified in Section 8.3.3. While the Investigator is not obligated to actively seek this information in former study participants /pregnant female partner, he or she may learn of an SAE through spontaneous reporting.

- Any female participant who becomes pregnant while participating in the study will discontinue study intervention or be withdrawn from the study.

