Appendix 3 Contraception and Barrier Requirements

Definitions:

Women of Child-Bearing Potential:

A woman is of childbearing potential (fertile) following menarche and until becoming postmenopausal unless permanently sterile, as specified below.

If fertility is unclear (e.g., amenorrhea in adolescents or athletes) and a menstrual cycle cannot be confirmed before the first dose of study intervention, consider additional evaluation.

Postmenopause:

Postmenopause is defined as no menses for 12 months without an alternative medical cause.

- A high FSH level in the postmenopausal range may be used to confirm a postmenopausal state in a female not using hormonal contraception or HRT. However, in the absence of 12 months of amenorrhea, confirmation with more than 1 FSH measurement (> 40 mIU/mL) is required.
- A female on HRT and whose menopausal status are in doubt will be required to use 1 of the nonestrogen hormonal highly effective contraception methods if she wishes to continue her HRT during the study. Otherwise, she must discontinue HRT to allow confirmation of postmenopausal status before study enrollment.

Permanent sterilization:

For this study, permanent sterilization includes:

- Documented hysterectomy
- Documented bilateral salpingectomy
- Documented bilateral oophorectomy

Documentation can come from the site personnel's review of the individual's medical records, medical examination, or medical history interview.

For individuals with permanent infertility due to an alternate medical cause other than the above, (e.g., Mullerian agenesis, androgen insensitivity), Investigator discretion applies to determine study entry.

Contraception Guidance:

CONTRACEPTIVES ALLOWED DURING THE STUDY INCLUDE:

Highly Effective Methods That Have Low User Dependency
 
• Implantable progestogen-only hormone contraception associated with inhibition of ovulation• IUD• IUS• Bilateral tubal occlusion• Vasectomized partner: a highly effective contraceptive method provided that the partner is the sole sexual partner of a WOCBP, and the absence of sperm has been confirmed. Otherwise, use an additional highly effective method of contraception. The spermatogenesis cycle is approximately 90 days.

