
Highly Effective Methods That Are User Dependent
 
• Combined (estrogen- and progestogen-containing) hormonal contraception associated with inhibition of ovulation
• Oral• Intravaginal• Transdermal• Injectable• Progestogen-only hormone contraception associated with inhibition of ovulation
• Oral• Injectable• Sexual abstinence: a highly effective method only if defined as refraining from intercourse during the entire period of risk associated with the study intervention. The reliability of sexual abstinence needs to be evaluated in relation to the duration of the study and the preferred and usual lifestyle of the participant.

Notes:
 
Contraceptive use by men or women is consistent with local regulations on the use of contraceptive methods for clinical study participants.
 
Highly effective methods are those with a failure rate of < 1% per year when used consistently and correctly. Typical use failure rates differ from those when used consistently and correctly.
 
If locally required, in accordance with CTFG guidelines, acceptable contraceptive methods are limited to those which inhibit ovulation as the primary mode of action.
 
Periodic abstinence (calendar, symptothermal, postovulation methods), withdrawal (coitus interruptus), spermicides only, and lactation amenorrhea method are not acceptable methods of contraception for this study. Male condom and female condom cannot be used together (due to risk of failure from friction).

Appendix 4 Adverse Events: Definitions and Procedures for Recording, Evaluating, Follow-up, and Reporting

AE Definition

- An AE is any untoward medical occurrence in a patient or clinical study participant, temporally associated with the use of study intervention, whether considered related to the study intervention or not.
- An AE can therefore be any unfavorable and unintended sign (including an abnormal laboratory finding), symptom, or disease (new or exacerbated) temporally associated with the use of study intervention. For surgical or diagnostic procedures, the condition/illness leading to such a procedure is considered as the AE rather than the procedure itself.

Events Meeting the AE Definition

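### Criterion 4a limits the condom option to partners who are not pregnant, so a man who chooses condoms has no express barrier duty toward a pregnant partner

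*Protocol*

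**What the plan says.** The introduction to criterion 4 (Protocol Section 5.1) makes the Investigator confirm each participant's agreement to suitable contraception and barriers, then points to the detail: "The contraception, barrier, and pregnancy testing requirements are below".

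Criterion 4a sets the rules for men. They apply during treatment and for at least one week after the final dose. Every man must refrain from donating sperm. He must also take one of two options:

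- Abstinence: "Abstain from intercourse with a WOCBP".
- A male condom, with one sub-bullet stating when: "When having sexual intercourse with a WOCBP, who is not currently pregnant, and instruct her to use a highly effective contraceptive method". The bullet goes on to refer to Appendix 3 for methods and gives possible condom failure as the reason.

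Appendix 3 defines the population to which both options refer: "A woman is of childbearing potential (fertile) following menarche and until becoming postmenopausal unless permanently sterile". Section 2.3.1 lists "Nonclinical Risks: Teratogenicity" among the tepotinib risks, with the rationale and mitigation cells redacted.

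**The concern.** The words about pregnancy fit the second half of the condom bullet, because there is no purpose in telling a pregnant woman to use contraception. They stand in the first half, however, in the clause that says when the condom is to be used. Read as written, they restrict the barrier too.

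An existing pregnancy is a case a barrier rule should address when teratogenicity is a named risk. Section 2.3.1 also reports a lack of genotoxicity in nonclinical studies. Among the visible text, then, the reproductive concern is harm to an embryo or fetus; this is an inference, because the supporting data are redacted. A rule that drops the barrier once the partner is pregnant leaves that concern uncovered, and no visible reason is given for doing so.

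There is also a practical difficulty. Section 5 permits no eligibility waivers, so the Investigator has to apply 4a literally. Beyond the sperm-donation ban, the text does not make clear what a man with a pregnant partner must agree to.

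**Working it through.** The plan gives no figure on this point and no calculation bears on the wording. The check sets the relevant texts side by side.

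**Step 1. Scope of each option in 4a**

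| Option | Partner named | Limited to non-pregnant partners? |
|---|---|---|
| Abstinence | a WOCBP | No (0 of 1 condition) |
| Male condom | a WOCBP who is not pregnant | Yes (1 of 1 condition) |

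**Step 2. Can a WOCBP be pregnant under this protocol?** Yes. The Appendix 3 definition ends only at menopause or permanent sterility. The condom bullet itself implies the same, since its qualifier would be redundant if pregnancy took a woman out of the definition. Abstinence therefore covers a pregnant partner and the condom option, as worded, does not.

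**Step 3. What follows under each possible reading**

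| Reading | Duty toward a pregnant partner |
|---|---|
| 1. The man selects one option for the whole study | If condoms: none stated |
| 2. The options apply partner by partner | Condom route closed; only abstinence remains |
| 3. The qualifier limits only the contraception instruction | Condom still required |

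These give no duty, the strictest duty and an intermediate duty. The text does not say which applies. The word order does not favor reading 3, because the qualifier comes before the instruction to the partner.

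**Step 4. Does other visible text settle it?**

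- Section 8.3.4: "Details of all pregnancies in female partners of male participants will be collected after the start of study intervention". It covers collection, reporting and follow-up, and sets no barrier rule.
- Appendix 3, definitions: terms only.
- Appendix 3, contraception guidance: a list of methods. Its one rule on male condoms is "Male condom and female condom cannot be used together (due to risk of failure from friction", which concerns combined use.

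None of these three places states a barrier rule for a pregnant partner.

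**Step 5. How many men could be affected?** Sections 1.1 and 9.2 cap enrollment at 18 participants of either sex. The number of men with a pregnant partner is not given, so the possible range is 0 to 18.

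**Step 6. How much of the period is spent in the unit?** The last dose of study intervention is itraconazole on Day 18, so the male requirements run to at least Day 18 + 7 = Day 25. Counting from the first dose gives 25 days. Participants are resident on Days 1 to 4 and 11 to 15, which is 4 + 5 = 9 days. The other 25 − 9 = 16 days are outside residence.

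**The case against.** The case for leaving the clause alone has four parts.

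1. **The answer may be in text we cannot see.** The mitigation cell of the teratogenicity row is redacted and is a natural place for partner precautions. Criterion 5 makes consent conditional on terms that may go further: "which includes compliance with the requirements and restrictions listed in the ICF and this protocol". This stands as a limit, and it cannot be claimed that the whole plan lacks such a rule. But 4a is not redacted, and a condom rule for pregnant partners elsewhere would conflict with it.

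2. **A general duty exists.** The introduction to criterion 4 asks for appropriate barriers where applicable, which gives the Investigator some room to require a condom. That sentence is followed at once by the statement that the requirements come below, so it leads back to the clause in question. It is not an express duty.

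3. **The gap appears only under reading 1.** Reading 2 is stricter than the proposed fix, and reading 3 is probably what was meant. That is fair, and it is why the point is put as a missing express duty or, at best, an ambiguity. If reading 3 was intended, the clause should say so.

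4. **Harm is not shown.** No semen-exposure data are visible. Tepotinib is given as two single doses, and participants are resident for about 72 hours after each, which limits contact when concentrations are likely to be highest. Partner pregnancies are collected until at least 3 months after the last dose. All this keeps the point small. Residence leaves 16 of the 25 days uncovered, however, and collecting outcomes does not prevent exposure.

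**Conclusion.** The concern holds as a minor point. Criterion 4a limits the condom, and not only the contraception instruction, to partners who are not pregnant, while abstinence has no such limit. A man who chooses condoms has no express barrier duty toward a pregnant partner, and the competing readings lead to materially different duties.

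The size of any risk cannot be quantified from the documents. The conclusion rests on the visible protocol text and on taking the Appendix 3 definition at face value. It does not assert that the redacted mitigation cell or the consent form is silent. The issue concerns fetal safety alone and does not touch the PK comparison, the confidence intervals or the sample size.

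**What to change.** Reword the male options in criterion 4a so that both have the same scope and the pregnancy qualifier attaches only to the contraception instruction. For example: throughout treatment and for a minimum of one week following the final dose, the man either abstains from intercourse with any WOCBP, including a pregnant partner, or uses a male condom with her; if she is not pregnant, he also tells her to use a highly effective method from Appendix 3. Check that the consent form says the same.

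The cost is one clause in Section 5.1. No visit, procedure or sample is added, and the existing duration is kept. The downside is a small extra burden on men whose partners are pregnant.

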5.2 Exclusion Criteria

Participants are excluded from the study if any of the following criteria apply:

Category	Criterion
Medical Conditions	
1. History or presence of clinically relevant respiratory, gastrointestinal, renal, hepatic, hematological, lymphatic, neurological, cardiovascular, psychiatric, musculoskeletal, genitourinary, immunological, dermatological, connective tissue diseases or disorders, as determined by medical evaluation.2. Participants with gall bladder removal or other relevant surgery of gastrointestinal tract (appendectomy is not considered as relevant).3. History of any malignancy except for adequately treated superficial basal cell carcinoma.4. History of epilepsy.
	
5. Ascertained or presumptive allergy/hypersensitivity to the active drug substance and/or excipients; history of anaphylaxis to drugs or serious allergic reactions leading to hospitalization or any other allergy reaction in general, which the Investigator considers may affect the safety of the participant and/or outcome of the study.6. Any condition, including findings in the laboratory tests, medical history, or other Screening assessments, that in the opinion of the Investigator constitutes an inappropriate risk or a contraindication for participation in the study or that could interfere with the study's objectives, conduct, or evaluation.
Prior/Concomitant Therapy	
7. Moderate or strong inhibitors or inducers of CYP3A4 and P-gp within 4 weeks prior to the first administration of study intervention.8. Use of any prescribed medicine or over-the-counter drug or dietary supplement, including herbal remedies, vitamins, and minerals, antacids and dietary supplements such as fish oils within 2 weeks or 5 times the half-life of the respective drug, whichever is longer, prior to the first administration of study intervention.

Category	Criterion
	
9. Administration of live vaccines or live-attenuated virus vaccines within 3 months prior to Screening. Administration of other types of vaccines (e.g., SARS-CoV-2 vaccines, final boost) is allowed until 1 week before admission to CRU.
 
Note: In case of clinical symptoms, the participant should be symptom-free for at least 1 week prior to admission to CRU.

Prior/Concurrent Clinical Study Experience	
10. Participation in the treatment phase of a clinical study within 60 days or 5 half-lives after last dosing of the previous study drug, whatever is longer, before administration of study drug.

Diagnostic Assessments	
11. Supine systolic blood pressure > 140 or < 90 mmHg, diastolic blood pressure > 90 or < 50 mmHg, and pulse rate > 90 or < 50 beats per minute at Screening and at admission on Day -1 (any abnormal blood pressure results may be repeated once and if the repeat result is within the normal range, it is not considered to have met the exclusion criterion). (Section 8.2.2)

	
12. 12-Lead ECG showing a QTcF > 450 ms, PR > 215 ms, or QRS > 120 ms at Screening and at admission on Day -1.

	
13. Creatinine clearance estimated glomerular filtration rate according to the Chronic Kidney Disease Epidemiology Collaboration Creatinine Equation (2009) < 90 mL/min at Screening.

	
14. History of alcoholism or drug abuse within 2 years prior to Screening, or positive for drugs of abuse, nicotine/cotinine or alcohol by the laboratory assays conducted during Screening and on admission on Day -1.

	
15. Positive for a) hepatitis B surface antigen, hepatitis B core antibody, hepatitis C antibody, or human immunodeficiency virus I and II tests at Screening; b) SARS-CoV-2 at Screening (by rapid antigen test) or at admission on Day -1 (by PCR test).

Category	Criterion
	
16. Clinically relevant findings (excluding minor, not clinically relevant excursions from normal ranges as judged by the Investigator) at Screening in biochemistry, hematology, coagulation, and urinalysis examinations for the age of the participant, as judged by the Investigator:
 
 • Alanine aminotransferase, aspartate aminotransferase: should not exceed the ULN \times 1.1 • Creatinine: above normal limits • Absolute lymphocyte count, absolute neutrophil count, absolute platelet count: below limit of reference range • Amylase and lipase above the upper limit of normal and/or signs/symptoms of pancreatitis.
Other Exclusions	
17. Contraindication to itraconazole (refer to Itraconazole USPI and SmPC): ventricular dysfunction such as congestive heart failure or a history of congestive heart failure, drug interactions (e.g., coadministration of a number of CYP3A4 substrates), pregnancy, hypersensitivity to itraconazole.

	
18. Donation or loss of more than 450 mL of blood in the 60 days prior to Screening, donation of plasma from 2 weeks prior to Screening, or platelets from 6 weeks prior to Screening.

	
19. Excessive consumption of xanthine-containing food or beverages (> 5 cups of coffee or equivalent a day) or inability to stop consuming caffeine at Screening and at admission on Day -1.

	
20. Consumption of an average weekly alcohol intake of > 14 units/week for men or > 7 units/week for women. 1 unit (12 g) of alcohol equals $\frac{1}{2}$ pint (285 mL) of beer or lager, 1 glass (125 mL) of wine, or $1/6$ gill (25 mL) of spirits.

	
21. Consumption of alcohol from 48 hours prior to first administration of study intervention.

	
22. Smoker (cigarettes, pipes, cigars, or others) or former smoker who stopped smoking for less than 6 months before the time of the Screening visit.

	
23. Intake of grapefruit, Seville orange, pomelo, grapefruit hybrids, exotic citrus fruit, cranberries or juices of these fruits, or St John's Wort, from 14 days prior to admission on Day -1.

	
24. Products containing poppy seeds (cake, rolls) may not be consumed within 48 hours before Screening and each admission until discharge.

Category	Criterion
	25. Inability to communicate or cooperate with the Investigator (e.g., language problem, illiteracy, poor mental status) or to comply with the requirements of the entire study, including dietary restrictions.
	26. Other factors, which in the opinion of the Investigator may interfere with study conduct.
	27. Legal incapacity or limited legal capacity.
	28. Participant is in custody by order of an authority or a court of law.

CRU=clinical research unit, CYP=cytochrome P450, PCR=polymerase chain reaction, P-gp=P-glycoprotein, ECG=electrocardiogram, SARS-CoV-2= severe acute respiratory syndrome coronavirus 2, SmPC=summary of product characteristics, ULN=upper limit of normal, USPI=United States prescribing information.

